#### *12.1.4 Exceptional rules*

In this clinical trial the following AEs/SAEs are excluded from the notification requirement:

- Serious or unexpected events which occur after enrolment, but before treatment was initiated
- Events with hospitalization planned before the inclusion to the trial (i.e. scheduled surgery)

#### *12.1.5 Suspected Unexpected Serious Adverse Reactions (SUSAR)*

A Suspected Unexpected Serious Adverse Reaction (SUSAR) is any suspected adverse reaction related to the study treatment that is both serious and unexpected.

“Unexpected” means that the nature and severity of the adverse reaction are not consistent with the information about the study medication in question set out in the reference safety information.

## **12.2 Treatment of (S)AEs**

All AEs should be treated appropriately. Such treatment may include changes in study drug treatment including possible interruption or discontinuation, starting or stopping concomitant treatments, changes in the frequency or nature of assessments, hospitalization or any other medically required intervention.

## **12.3 Assessment of AEs and SAEs**

As far as possible, each AE should be evaluated to determine:

- the severity grade (assessment of intensity)
- whether it constitutes a SAE (see 12.1.3)
- its relationship to the study drug (assessment of causality)
- its duration (start and end dates or if continuing at final exam)
- action taken (no action taken; study drug dosage adjusted/temporarily interrupted; study drug permanently discontinued due to this AE; hospitalization)

### *12.3.1 Assessment of intensity*

We will apply the following definitions according to the Common Terminology Criteria for Adverse Events (CTCAE) grading:

Grade 1 Mild; asymptomatic or mild symptoms; clinical or diagnostic observations only; intervention not indicated.

Grade 2 Moderate; minimal, local or noninvasive intervention indicated; limiting age-appropriate instrumental ADL (Activities of daily living).

Grade 3 Severe or medically significant but not immediately life-threatening; hospitalization or prolongation of hospitalization indicated; disabling; limiting self-care ADL.

Grade 4 Life-threatening consequences; urgent intervention indicated.

Grade 5 Death related to AE.

Seriousness (severity grade) shall be determined according to the definition above. Furthermore, medical and scientific judgment should be exercised in deciding whether expedited reporting is appropriate in other situations, such as important medical events that may not be immediately life-threatening or result in death or hospitalization but may jeopardize the subject or may require intervention to prevent one of the other outcomes listed in the definition above. These should also usually be considered serious. Examples of such events are intensive treatment in an emergency room, or at home for allergic bronchospasm, blood dyscrasias or convulsions that do not result in hospitalisation, or development of drug addiction or drug abuse.

### *12.3.2 Assessment of causality*

To assess causality between administration of the IMP and the Adverse Event the following definitions apply:

Sure: The reaction comprehensively follows the administration of the IMP in the right timeframe or can be measured in body tissues or fluids or represents a known or expected response to the study medication or disappears after discontinuation or dose reduction and reoccurs after re-exposure.

Probable: The reaction comprehensively follows the application of the IMP in the right timeframe or represents a known or expected response to the study medication or disappears after discontinuation or dose reduction and cannot be explained by known characteristics of the patient's disease.

Possible: The reaction comprehensively follows the application of the IMP in the right timeframe or represents a known or expected response to the study medication, but could easily be caused by other factors.

Not related: Adequate Information supporting the assumption that there is no causality

Cannot be evaluated: The causality cannot be determined.

## **12.4 Documentation of AEs and SAEs**

All AE and SAEs will be documented, no matter if the investigator suspects a causal connection to the IMP or not. The event will be recorded in the eCRF.

Out of normal range laboratory data and ECG abnormalities will be analyzed concerning their clinical relevance by the subinvestigator – and if relevant documented as an AE itself. Related signs, symptoms, and laboratory changes will be summarized to a specific disease. The documentation will include the type of event, start, duration, severity, causality, and action taken.

SAEs need to be documented on a separate SAE form (see 12.5.1). All SAEs need to be followed until they subside or stabilize.

The Sponsor/Sponsor representative will carefully document all Adverse Events (AEs) reported by the investigator.

## **12.5 Reporting of SAEs and SUSARs**

### *12.5.1 Reporting of SAEs / Contact for SAE reporting*

Every event will be documented on a record form and will immediately be sent to the given address. If at that point all required information is not available, succeeding records will be sent. In the event of death, a copy of the autopsy record should be added.

The investigator shall promptly (at the latest within 24 h) notify the Sponsor/Sponsor representative of the occurrence of a Serious Adverse Event after becoming aware and subsequently provide the Sponsor/Sponsor representative with a detailed written report.

Contact details for SAE reports:

Charité Universitätsmedizin Berlin  
Koordinierungszentrum für klinische Studien /KKS Charité  
Central Pharmacovigilance KKS Charité  
[contact]  
Email: [contact]

Personal data shall be pseudonymized before transmission using the identification code of the data subject.

The report must include the following minimal criteria:

- Patient-ID
- Name of reporter/investigator
- Information on event (term, case narrative, duration)
- Assessment of severity and causality (relationship to study drug/study procedure/concomitant medication/other circumstances)

---

 GCP-V §12 (4), and 2011/C 172/01 (CT-3), 4.3.1, 29.

### ***12.5.2 Reporting of Suspected Unexpected Serious Adverse Reactions (SUSARs)***

Before reporting a SUSAR (Suspected Unexpected Serious Adverse Reactions) the subject will be unblinded. The Sponsor/Sponsor representative will report all suspicious cases of SUSARs which had been occurred in one of clinical trials conducted by the same Sponsor with the same drug substance/IMP to the relevant Ethics Committee, the relevant regulatory authorities and to relevant regulatory authorities of other European member states and other contracting states of the EWR agreement, if the study is run in their territory immediately, at the latest 15 days after it becomes known. He will also inform all investigators involved in the trial.

In case of a fatal or life threatening SUSAR the Sponsor/Sponsor representative will report all information relevant for judging the event immediately, at the latest 7 days after the event becomes known to the relevant Ethics Committee, the relevant regulatory authorities and to relevant regulatory authorities of other European member states and other contracting states of the EWR agreement, if the study is run in their territory as well as to all investigators involved in the trial. After a further 8 days all further relevant information must be available.

### ***12.5.3 Other safety issues requiring expedited reporting***

The Sponsor/Sponsor representative will immediately, at the latest 15 days after it becomes known report all circumstances that require a revision of the risk-benefit analysis to the relevant Ethics Committee, the relevant regulatory authorities and to relevant regulatory authorities of other European member states and other contracting states of the EWR agreement, if the study is run in their territory. This especially includes:

- Singular cases of expected severe adverse events with an unexpected outcome.
- Increased incidence of expected severe adverse events that are judged as being clinically relevant.
- Events related to study procedures or development of the study medication, which could affect a subject's safety.

All person-related data will always be transmitted pseudonymized.

## **12.6 Follow-up of adverse events**

Once an AE is detected, it will be followed until its resolution or stabilization, and assessment will be made at each visit (or more frequently, if necessary) of any changes in severity, the suspected relationship to the study, the interventions required to treat it and the outcome.

Follow-up information is sent to the same address to which the original SAE Report Form was sent, using a new SAE Report Form stating that this is a follow-up to the previously reported SAE and giving the date of the original report. Each re-occurrence, complication, or progression of the original event will be reported as a follow-up to that event regardless of when it occurs. The follow-up information will describe whether the event has resolved or continues, if and how it was treated, whether the patient continued or withdrew from study participation.

For a follow-up report to the authorities, the investigator may be required to collect further information for a detailed description and a final evaluation of the case, including copies of hospital reports, autopsy reports, or other relevant documents.

## **12.7 Data Monitoring Committee**

We will seek advice from independent experts in the field who have agreed to serve on the Data and Safety Monitoring Board (DSMB):

- [name]. [name] (methods expert/epidemiologist), Vrije Universiteit Amsterdam

- [name]. [name] (clinician), Zentralinstitut für Seelische Gesundheit, Mannheim
- [name]. [name] (clinician), Klinik für Psychosomatik und Psychotherapeutische Medizin Universitätsmedizin Rostock
- [name] (patient representative), Deutsche Depressionsliga

To ensure that the patients' perspective will be present at all DSMB meetings as recommended by the European Patient Academy [77], [name], vice-chair of the "Deutsche Depressionsliga" has kindly agreed to serve on the DSMB. The DSMB will regularly (once a year) assess safety data during the course of this study and their primary interest is the safety of study participants and integrity and validity of collected data.

## **13. Documentation**

### **13.1 Source Data and Study Files**

The investigator must maintain source documents for each patient in the study (see 15.1).

### **13.2 Case Report Forms (CRF)**

Investigators or their designee must enter the information required by the protocol onto the electronic case report forms - eCRF (see 15.2).

### **13.3 Investigator Site File (ISF)**

All essential documents will be kept in the Investigator Site File, which will be stored at the study sites in accordance with ICH GCP chapter 8.

### **13.4 Drug accountability / Flow of study medication**

Study medication will be provided by Charité pharmacy. Receipt of study medication will be documented in each study site (date, number of medication received, charge-ID, etc.) by the investigator. The individual patient will receive the medication from the subinvestigator. This will be documented in the drug account (date, charge-ID). Medication that is not used and empty medication boxes will be stored until final closure of the drug account by the clinical study monitor.

## **14. Quality management**

### **14.1 Control of trial progress and data quality**

The study sites will be monitored by a clinical study monitor to ensure the quality of the data collected. The objectives of the monitoring procedures are to ensure that the trial subject's safety and rights as a study participant are respected, that accurate, valid and complete data are collected, and that the trial is conducted in accordance with the trial protocol, the principles of GCP and local legislation.

#### **14.1.1 *Monitoring, Data Quality Assurance***

All investigators agree that the monitor regularly visits the study site and assure that the monitor will receive appropriate support in his activities at the study site. The declaration of informed consent includes a statement to the effect that the monitor has the right – while observing the provisions of data protection legislation – to compare the case report forms (eCRFs) with the trial

subject's study files (doctor's notes, ECGs, laboratory printouts etc.). The investigator will secure access for the monitor to all necessary documentation for trial-related monitoring. The aims of the monitoring visits are as follows:

- To check the declarations of informed consent.
- To monitor trial subject safety (occurrence and documentation/reporting of AEs and SAEs).
- To check the completeness and accuracy of entries on the eCRF.
- To validate the entries on the eCRF against those in the source documents (source data verification, SDV).
- To evaluate the progress of the trial.
- To evaluate compliance with the trial protocol.
- To assess whether the trial is being performed according to GCP at the study site.
- To discuss with the investigator aspects of trial conduct and any deficiencies found.

A monitoring visit report is prepared for each visit describing the progress of the clinical trial and any problems (e.g. refusal to give access to documentation).

The investigators allow the monitor to have access to any or all of the study materials needed for source data verification and proper review of the study progress. At all times, the Sponsor/investigators/monitors will maintain the confidentiality of the study documents. Furthermore, problems with inconsistent and incomplete data will be discussed. By signing the declaration of informed consent, the participants allow access to their documents.

#### *14.1.2 Audits / Inspections*

Authorized representatives of the Sponsor, a regulatory authority, or an Independent Ethics Committee (IEC) may visit the center to perform audits or inspections, including source data verification. The purpose of a Sponsor audit or inspection is to systematically and independently examine all study related activities and documents to determine whether these activities were conducted, and data were recorded, analyzed, and accurately reported according to the protocol, Good Clinical Practice (GCP), guidelines of the International Conference on Harmonisation (ICH), and any applicable regulatory requirements.

With the signature in the protocol, the investigators confirm that auditors and health authority inspectors may have access to the study documentation and accordant medical records. Auditors and inspectors are bound by professional confidentiality and may not pass on any personal information that comes to their knowledge. In the course of audits or inspections, data in the case report forms will be compared with the data for medical records. All the documentation held by the investigators within the scope of the clinical trial, as well as the drug logs of the study medications will be verified.

### **14.2 Standardisation and validation**

All rating scales have previously been standardized and validated.

### **14.3 Reference institutions**

Not applicable.

## **15. Data entry und data management**

Patient related data will be recorded in study files (source data) under the participant's real name. The information required by the protocol will be entered onto the electronic case report forms

(eCRF - secuTrial) under a pseudonym. Every patient will receive a patient number / pseudonym which will be unique for this individual patient (see 9.3).

### **15.1 Source Data and Study Files**

The investigator must maintain source documents for each patient in the study, consisting of all demographic and medical information, including laboratory data, electrocardiograms, and all assessments and keep them together with the signed informed consent form in designated study files. The information in original documents and records defined as Source Data will be reviewed by the Monitor for Source Data Verification.

### **15.2 Data collection / Case Report Form (CRF)**

Investigators or their designee must enter the information required by the protocol onto the electronic case report forms (eCRF - secuTrial®). Data items from the eCRF are entered into the study database. All entries to the eCRF must be made as described in the electronic case report form manual. All information on eCRF must be traceable to source documents in the study file.

A clinical study monitor will review the eCRF and compare the content to the source data. In addition, the investigator or designated colleague will provide access to designated Sponsor representative(s) for the periodic review of source documents (e.g. hospital and clinic records) to assure accuracy and completeness of the eCRF.

### **15.3 Data management**

Data required for the analysis will be acquired and transferred electronically to a central database at the KKS Charité by means of an electronic data capture system (EDC) - secuTrial®.

The secuTrial® Software solution of interActive Systems (iAS) is a worldwide reachable web-based system (remote data entry [RDE]). The system operates according to the principle of online data capture and is in compliance with the FDA 21 CFR Part 11 and ICH-GCP. In addition, it contains further functions to perform plausibility, consistency and range checks of the study data.

The log-in in the system requires a previous authentication for access and runs by a secure data transfer-protocol (SSL) to exclude any improper manipulation of data by unauthorized parties. The system will automatically keep an audit trail of all entries and corrections to the eCRF.

The secuTrial® Software solution is based on an Oracle database that does not allow direct access. All access rights of study staff will be defined according to their trial functions. The defined access rights will e.g. allow to read or to enter study data depending on their functions (Monitor, clinical investigator, etc.).

Query management is an integrated part of this RDE system. This function allows the communication between the Monitor and study staff. In case of errors or improper data, the responsible person of study staff will get queries (messages) to correct the errors or to check improper data on the eCRF.

The trial data will be stored digitally on a remote server with daily backups. After end of study all data will be exported for checks of consistency and plausibility. After performing the checks, the data matrix will be transferred in pseudonymized form for the statistical evaluation.

## 16. Statistical Analysis

### 16.1 Hypotheses

#### 16.1.1 *Primary hypothesis*

Simvastatin (40 mg/d) add-on to the standard antidepressant Escitalopram (20 mg/d) improves depression to a greater extent over 12 weeks than add-on placebo in patients with comorbid obesity and major depression

#### 16.1.2 *Secondary hypotheses*

[figure not shown]
Add-on Simvastatin (40 mg/d) to standard antidepressant Escitalopram (20 mg/d) will improve:

- 1) response rates, and remission rates,
- 2) patients' impression of change, clinician's impression of severity and change, quality of life, social functioning, self-report depression,
- 3) lipid values,
- 4) mitochondrial and cellular function of immune cells

to a greater extent over 12 weeks than adjunct placebo in patients with major depression and comorbid obesity.

### 16.2 Sample size estimation

So far, there are three small pilot RCTs in depressed patients (sample sizes ranging from  $n = 48$  to  $n = 68$ ) that have all found statistically significant beneficial effects of add-on statins vs. placebo with large, clinically relevant effect sizes. A meta-analysis [2] of these trials has found a standardized mean difference between add-on statins and add-on placebo of  $-0.73$  (95 % confidence interval  $-1.04$  to  $-0.42$ ,  $p < 0.001$ ). However, it is well-known that initial studies tend to overestimate the true effect size [78]. Therefore, we conservatively assume a standardized treatment difference (also known as Cohen's  $d$ ) of  $0.5$ , which is supported by the findings of all pilot RCTs [36, 79, 80]. Given a standard deviation of 6-8 points on the MADRS, as commonly observed in RCTs in this population [81-83], a standardized effect size of  $0.5$  translates into a mean difference of 3-4 points, which is considered clinically relevant because it is about twice as large as the minimal clinically important difference of 1.6 to 1.9 points that has been reported [84]. Thus, a sample size of 64 patients per group gives a power of 80% for a comparison of the mean changes in MADRS score from baseline to week 12 between the two treatment groups using a two-sample t-test at the usual two-sided level of 5%. As the analyses will be adjusted for baseline scores the actual power is likely to be higher; this will be confirmed in a blinded sample size review once 50% of the patients have reached week 12 [85]. Accounting for about 20% dropout, we aim to recruit 80 patients per group (i.e. 160 patients in total). Based on sex-specific prevalence rates and recruitment in our earlier studies [86, 87], we expect that about two thirds of the sample will be women. This will allow gender-specific analyses.

**Figure 4:** Study flow chart according to CONSORT. We assume that we need to screen  $N = 1125$  patients aged 18 - 65 with major depression according to Diagnostic and Statistical Manual of Mental Disorders (DSM) 5 and obesity (body mass index  $\geq 30$ ) for eligibility at 8 recruiting centers to randomize  $n = 160$  participants. The sample size and assumed dropout rate (20%) is conservatively based on three earlier pilot RCTs of add-on statin to SSRI treatment in depressed patients [1-3].

### 16.3 Definition of population for analysis

The primary analysis population will be the intention-to-treat (ITT) population. The ITT population will include all randomized patients. We will repeat the analyses in the per-protocol sample.

### 16.4 Analysis of primary and secondary endpoints

The primary analysis will compare MADRS changes from baseline to week 12 between the Simvastatin and placebo group by Gaussian linear models for repeated measures (so-called MMRM) with intervention, center, time (week 1, 2, 4, 8, and 12), and intervention-by-time interaction as factors, and baseline MADRS score as covariate. The error terms are assumed to follow a multivariate normal distribution with unstructured covariance. Least squares mean changes from baseline will be reported for both groups with 95% confidence interval (CI) as well as the difference between the least squares treatment group means with 95% CI and p-value testing the null hypothesis of no treatment effect. Although the model described above is robust to a certain extent to missing data, sensitivity analyses will be performed as supporting analyses including multiple imputation and last-observation-carried-forward (LOCF). The latter will also facilitate comparison with previous trials.

The analyses of all secondary endpoints and safety parameters will have an exploratory character and will therefore not be adjusted for multiple testing. The secondary efficacy endpoints MADRS-response and MADRS-remission, and MADRS-MCID within 12 weeks will be analyzed by logistic regression models with intervention and center as factors and baseline MADRS as covariate. The treatment effects will be reported as odds ratios with 95% CI and p-values testing the null hypotheses of no treatment effect. The analyses of continuous secondary efficacy endpoint as well as SOFAS, and EQ-5D-3L will follow the same lines as the primary outcome.

We will repeat the analyses in the per-protocol sample.

All details of the statistical analyses including definitions of the analyses populations will be specified in the statistical analysis plan, which will be finalized before database lock and unblinding. All statistical analyses will be carried out using SAS software (SAS Institute Inc., Cary, NC, USA) or the R package.

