
Statistical analysis
	
Primary efficacy (confirmatory) endpoint:
 
The primary analysis will compare MADRS change from baseline to week 12 between the Simvastatin and placebo group by Gaussian linear models for repeated measures (so-called MMRM) with intervention, center, time (week 1, 2, 4, 8, and 12), and intervention-by-time interaction as factors, and baseline MADRS score as covariate. The primary analysis population will be the intention-to-treat (ITT) population.
 
Secondary efficacy (exploratory) endpoints:
 
The secondary efficacy endpoints include the percentages of MADRS-response, MADRS-remission, and MADRS-MCID within 12 weeks that will be analyzed by logistic regression models with intervention and center as factors and baseline MADRS as covariate. The analyses of secondary efficacy endpoint BDI-II will follow the same lines as the primary outcome. The analyses of safety parameters and all secondary endpoints will have an exploratory character.

Pharmacological-toxicological evaluation
	
Both Simvastatin and Escitalopram are approved for several indications since decades. The respective “latest version of German Fachinformation” for each medication are in the Investigator site file (ISF).

Risks, adverse drug reactions, drug interactions,
	
Simvastatin is the IMP that will be tested versus placebo as add-on to standard antidepressant medication with Escitalopram, which will be given open label to each patient. We list the risks and potential adverse drug

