Secondary Exploratory	Mitochondrial and cellular function of immune cells	Laboratory values	Immune function	Mean Change from Baseline	Continuous

The time point for the evaluation of the secondary endpoints is 12 weeks. The secondary efficacy endpoints MADRS-response and MADRS-remission within 12 weeks will be analyzed by logistic regression models with intervention and center as factors and baseline MADRS as covariate. The analyses of continuous secondary efficacy endpoint BDI-II, and continuous secondary exploratory endpoints SOFAS, and EQ-5D-3L will follow the same lines as the primary outcome. The analyses of safety parameters and all secondary endpoints will have an exploratory character.

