### 6.2.1 *Inclusion criteria*

- Written informed consent is present
- The patient has the capacity to give consent (He/she is able to understand the nature and anticipated effects/side effects of the proposed medical intervention)
- The patient has a major depressive episode according to DSM 5 (Diagnostic and Statistical Manual of Mental Disorders 5th Edition)
- The patient has a score of  $\geq 18$  in the Montgomery-Asberg Depression Rating Scale (MADRS)
- The patient has a body mass index  $\geq 30$
- The patient's age is between 18 and 65 years ( $\geq 18$  und  $\leq 65$ )
- The patient has not given childbirth within the 6 months prior to study entry and is not breastfeeding
- In case of non-psychotropic medication:  
The patient received stable pharmacological medication for at least 14 days prior to study entry (any changes in medication dose or frequency of therapy must be answered with no)
- The patient did not take antidepressants during the last 7 days prior to study entry (discontinuation of effective medication to enable study participation is prohibited)
- The patient did not receive prior treatment with Escitalopram in index episode
- The patient had less than three (<3) trials with antidepressants in index episode
- The patient does not have a history of non-response to Escitalopram
- The patient did not receive treatment with ketamine, electroconvulsive therapy (ECT) or other stimulatory treatments in index episode
- The patient does not meet any of the following criteria:
  - schizophrenia
  - schizoaffective disorder
  - bipolar disorder
- The patient is not diagnosed with dementia and does not have moderate or severe impairment of general cognitive function according to clinical impression
- The patient does not have clinically relevant elevated liver enzymes [GOT or GPT  $> 3$  x upper limit normal (ULN)] and does not have elevated Carbohydrate Deficient Transferrin (CDT)  $\geq 2.4$  %
- The patient does not meet the criteria for alcohol use disorder (DSM-5: 303.90; ICD-10: F10.20) or substance use disorder (DSM-5: 304; ICD-10: F11.20 – F19.20) in M.I.N.I. for DSM-5 and a urine/serum drug screening is negative (except for benzodiazepines and opiates)
- The patient does not have a history of suicide attempt
- The patient does not have diagnosed epilepsy or increased bleeding diathesis or a history of angle closure glaucoma or other glaucomas

- The patient did not have bariatric surgery prior to study entry

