**Escitalopram (standard antidepressant that each patient will receive):**

- 10 mg/d for first two weeks, then increase to 20 mg/d until end of study

- If side effects occur in the first two weeks, 10 mg/d Escitalopram can be reduced to 5 mg/d until the next visit, then ideally increased to 10 mg/d again unless side effects persists.
- If side effects occur after the increase to 20 mg/d, Escitalopram can be reduced to 10 mg/d until next visit, then ideally increased to 20 mg/d again unless side effects persists.

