### **16.6 Interim analyses and endpoints for premature study termination**

As the analyses will be adjusted for baseline scores the actual power is likely to be higher than 80 %. To confirm this in an interim analysis, a blinded sample size review will be carried out once 50 % of the patients have reached week 12. Based on blinded estimates of the mean square error and the dropout rate the required sample size will be recalculated and the sample size will be adjusted up to a maximum total sample size of 240 patients, if necessary.

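### The primary MMRM fits one baseline MADRS slope to all five visits; a baseline-by-time term would protect week-12 precision at almost no cost

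*Combined protocol and SAP*

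**What the plan says.** Section 16.4 lists the fixed effects of the primary model as "intervention, center, time (week 1, 2, 4, 8, and 12), and intervention-by-time interaction as factors, and baseline MADRS score as covariate", with an unstructured error covariance. The Synopsis gives the same terms: "center, time (week 1, 2, 4, 8, and 12), and intervention-by-time interaction as factors, and baseline MADRS score as covariate". No section adds a baseline-by-time term. The confirmatory contrast is the week-12 difference alone.

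Section 16.2 sizes the trial on an unadjusted two-sample t-test and then remarks: "As the analyses will be adjusted for baseline scores the actual power is likely to be higher". Section 16.6 repeats that expectation and adds a blinded review: "Based on blinded estimates of the mean square error and the dropout rate the required sample size will be recalculated", up to 240 patients in total.

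Section 16.4 leaves further detail to a statistical analysis plan "which will be finalized before database lock and unblinding". The same model form carries over to BDI-II and, in section 5.2.2, to the "continuous secondary exploratory endpoints SOFAS, and EQ-5D-3L will follow the same lines as the primary outcome".

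**The concern.** A single baseline coefficient is the right adjustment for week 12 only if the slope of the score on baseline is the same at every visit. If it is not, the fitted common slope is a weighted compromise, and in this design it tends to lean toward the early visits. Week 12 is then adjusted with a slope that does not fit it, and some baseline variation stays in the week-12 residual.

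Unequal slopes are possible here. Weeks 1 and 2 fall in the initial Escitalopram phase (section 7.2.4: "10 mg/d for first two weeks, then increase to 20 mg/d until end of study"), so early scores may stay closer to baseline than week-12 scores do. There is also a force the other way. The entry threshold of MADRS 18 limits the spread at baseline but not later, and a later SD that grows while the correlation falls can leave the slope unchanged.

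At stake is part of the power gain the plan expects from baseline adjustment. If the blinded review takes its mean square error from this model, it may detect the loss, but it would then recover with extra patients what data already collected could supply.

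**Working it through.** **The plan's own figure.** Inputs from section 16.2: d = 0.5, two-sided 5%, 64 per group. The noncentrality is 0.5 × √(64/2) = 2.83 on 126 degrees of freedom. Power is 80.1% (79.5% with 63 per group), and 64/0.8 = 80. The figures reproduce, and no baseline covariate enters them.

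**Formula.** Let s_j be the slope at visit j (correlation with baseline × SD_j / SD_b), and S the residual covariance when each visit has its own slope. With complete data the common slope is b = (1'S⁻¹s)/(1'S⁻¹1). The week-12 residual variance is:

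- visit-specific slopes: S55
- one slope: S55 + SD_b²(s12 − b)²
- unadjusted change score: S55 + SD_b²(s12 − 1)²

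Apart from degrees of freedom, visit-specific adjustment is therefore never less precise than the change score. One common slope can be, when b lies further from s12 than 1 does.

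**Examples (assumed values).** Take baseline SD 5, SD 6 at every visit, correlation with baseline falling evenly by visit from 0.7 to 0.3, and between-visit correlation 0.7 to the power of visits apart. The slopes run from 0.7 × 6/5 = 0.84 to 0.3 × 6/5 = 0.36, and b = 0.67. S55 = 36 × (1 − 0.09) = 32.76. With one slope the variance is 32.76 + 25 × (0.36 − 0.67)² ≈ 35.2, a ratio of 1.07. With the effect set so that the change-score t-test has 80% power, power is 87.2% as written and 89.4% with visit-specific slopes.

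By contrast, correlations of 0.6 to 0.4 with SDs of 5.5 to 8 give slopes of 0.66 and 0.64, and nothing is lost.

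**Grid (all assumed except the week-12 SD range, from section 16.2).**

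- Baseline SD 5 or 6; week-12 SD 6, 7 or 8.
- Earlier SDs either equal to the week-12 SD, or rising to it from the baseline SD in five equal steps.
- Correlation with baseline 0.5–0.8 at week 1 and 0.2–0.7 at week 12, falling by 0–0.5, evenly by visit or by week.
- Between-visit correlation 0.7 or 0.8 to the power of visits apart.

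This gives 814 distinct structures, each with 64 per group, complete data and the change-score test at 80% power.

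| Week-1 minus week-12 slope | Structures | Median loss (points) | Maximum |
|---|---|---|---|
| within 0.1 either way | 166 | 0.02 | 0.25 |
| 0.1–0.3 | 300 | 0.5 | 2.0 |
| 0.3–0.5 | 236 | 1.8 | 5.5 |
| above 0.5 | 76 | 4.0 | 8.0 |

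In the remaining 36 the slope rises by more than 0.1, and the loss is at most 1.3 points.

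- **SD pattern.** All 76 structures in the last row have the week-12 SD already at week 1. With SDs rising from baseline, the median loss is 0.4 and the maximum 5.0.
- **Absolute power.** The written model keeps at least 80% in 755 of 814 structures. The other 59 return to at least 80% with the added term. The lowest value is 76%, but power falls below 79% only where the week-1 slope is 1 or more; otherwise the lowest is 79.1%.
- **In patients.** For correlation falls of 0.4–0.5 (220 structures) the median variance increase is about 9%, and 0.09 × 64 ≈ 6 evaluable patients per group. For smaller falls (594 structures) the median is under 1%, or less than one patient per group; the power loss is under 1 point in 493 of them.

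**Simulation.** REML with estimated unstructured covariance, 8 centers, 64 per group, complete data, 8,000 trials per structure; power as written versus with baseline by time:

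- near-equal slopes: 82.3% vs 82.1%
- correlation 0.7 to 0.5 (SD 7): 84.6% vs 85.1%
- 0.7 to 0.3 (SD 6): 87.4% vs 89.0%
- 0.8 to 0.3 (SD 7, even by week; the grid's extreme): 82.9% vs 89.9%

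Mean estimates were within 0.01 points of the truth under both models.

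A separate simulation used 80 per group with 20% dropout completely at random (1,500 trials). It gave 85.7% vs 86.8% for slopes falling from 0.7 to 0.4, and 83.6% vs 87.9% for 0.9 to 0.3, again without bias.

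**The case against.** One common slope is a valid, prespecified model. The plan says only that adjusted power is likely to exceed 80%, and most assumed structures bear that out. Nothing in the documents shows that the slopes differ, the largest losses need a particular SD pattern, and section 16.4 defers detail to a later SAP. All of this stands, and it is why the point is optional. The deferral does not remove it, though: the protocol states the model's terms explicitly, and an SAP that follows them would keep the single slope.

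A reader might infer more than this. Three stronger readings are not supported:

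- **That the trial is underpowered.** The 64 and 80 per group rest on an unadjusted t-test. The 76% floor needs a week-1 slope of 1 or more. A second grid, set directly in slopes with baseline SD 3–6, had a lowest written-model power of 79.8%, although its steepest pattern (0.9 to 0.2) lost up to 12.4 points of the adjustment gain.
- **That the estimate is biased.** Under randomization it is not, and the simulations agree. Dropout that depends on outcome or arm was not examined.
- **That about six patients per group are wasted.** That figure belongs only to correlation falls of 0.4–0.5.

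**Conclusion.** The point holds as a small efficiency matter. The written model imposes one baseline slope on five visits and may not deliver all the precision at week 12 that baseline adjustment can give. The loss is negligible when slopes are close, typically half a point of power for a modest fall in slope, and several points only for a steep one. The analysis stays valid and the planned sample size stands. The size rests wholly on assumed SDs, slopes and correlations, because the documents supply only the 6–8 point SD; the grid also assumes complete data. The case for acting is the asymmetry: a cost near zero if slopes are equal, and a useful gain if they are not.

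**What to change.** Add baseline MADRS by time to the primary MMRM in sections 1 and 16.4 and in the SAP, before database lock and unblinding. Add the matching baseline-by-time term for BDI-II, SOFAS and EQ-5D-3L. As an optional clarification, say in section 16.6 that the blinded mean square error is the week-12 residual variance from that model.

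The cost is wording only, with no new data. The term uses four degrees of freedom for MADRS and BDI-II (five post-baseline visits), and one for SOFAS and EQ-5D-3L (weeks 4 and 12 only). If the slopes are in fact equal, the price is about 0.2 power points.
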